**Number: NCT05859243**

**Date: 16, May, 2023**

**Abstract:** The aging is a natural, progressive and multifactorial process that affects all the organism. Whereas, generally (but not necessarily) the aging process is associated with chronic diseases, the health aging premiss is not the absence of disease, but the opportunities to continue experiencing situations that are considered valuable over the years. Thus, independence becomes one of the most important outcomes for maintaining a great quality of life throughout the aging process. Functional independence is influenced by several factors and an active lifestyle can act directly in this aspect. In this sense, the World Health Organization recommends, in addition to the practice of physical activities, the regular practice of structured physical exercise for older people. In this logic, the combination of strength training and aerobic training (i.e., concurrent training) has been a widely used intervention for health outcomes. In addition, dance has been a physical practice well described in the literature as an aerobic activity that can bring several health benefits, especially for older people. Thus, dance with strength training seems to be an interesting option for a complete physical training program. Thus, the aim of the present study is to identify and compare the impacts of traditional concurrent training and concurrent training consisting of strength training combined with dance classes on functional performance, cognitive function and quality of life of older people.

**Key-words:** aging, functional capacity, physical activities.

## INTRODUCTION

The world population aging is a reality. The World Health Organization (WHO, 2022b) affirm that until 2050, 2.1 billion people will be considered old individuals. The aging is a natural, progressive and multifactorial process that affects the organism entirely (LITVOC & BRITO, 2004). This process provoked muscle alterations that could decrease the functional performance (NETTO, 1999).

Whereas, generally, but not necessarily, the aging process is associated with chronic diseases, the healthy aging premise is not the absence of diseases, but is the opportunities to continue experiencing situations that are considered valuable over the years (WHO, 2020a). Thus, functional independence becomes one of the most important outcomes for the quality of life maintenance throughout the aging process.

Functional independence can be affected by different factors, such as the presence of diseases, injuries and alterations related to aging (WHO, 2020a). In that regard, active lifestyle can attenuate functional independence, whereas physical activity can prevent and attenuate chronic diseases, increase the mobility, decrease depressive symptoms and decelerate cognitive declines (IZQUIERDO *et al.*, 2021).

About functional performance, muscle strength is one of the most important factors, whereas it is strongly related to sarcopenia and, consequently, to functional independence. Though strength training alone can not be beneficial for balance related outcomes (CADORE *et al.*, 2013), besides having minimal effects on cardiorespiratory capacity compared to aerobic training (CADORE *et al.*, 2011). Balance and cardiorespiratory capacity are, respectively, important to prevent falls and to maintain functional independence in old people (BLANCO-RAMBO *et al.*, 2022; SHEPHARD, 2009). Therefore, it is necessary to include others training modalities in the routine of old individuals.

In that regard, the combination of strength and aerobic training (i.e., concurrent training) has been widely used. This modality unifies aerobic and strength training in one session, and can promote the same benefits as both training performed separately in addition to optimizing the time in training (CADORE & IZQUIERDO, 2013). Nonetheless, traditional concurrent training does not include exercises for other physical components recommended by WHO (2020b) for old individuals, like balance exercises.

Though, dance has been a physical activity well described in the literature as an activity that can bring many health benefits, especially for the old people. Dance can increase cardiorespiratory capacity (RODRIGUES-KRAUSE *et al.*, 2016), improve dynamic and static balance (BLANCO-RAMBO *et al.*, 2022), gait ability, mobility and physical performance (FERNÁNDEZ-ARGÜELLES *et al.*, 2015), in addition to decrease motor symptoms of Parkinson's disease, improve cognition (CARAPELLOTTI *et al.*, 2020), in addition to being a fun, pleasurable and common activity among the elderly (VERGHESE, 2006).

However, despite the many benefits that dancing can provide to the older population, it causes little or no improvement in muscle strength.(SERRA *et al.*, 2016).Thus, using dance together with strength training seems to be an interesting option for a complete physical training program for old peoples, following the WHO recommendations. However, to our knowledge, studies using the combination of these two modalities (i.e., strength training and dance) as an alternative for improving neuromuscular, cardiorespiratory and cognitive performance of old individuals have not yet been carried out.

## OBJECTIVES

The general objective of this randomized controlled clinical trial is to identify and compare the impacts of traditional concurrent training and concurrent training consisting of strength training combined with dance classes on functional performance, cognitive function and quality of life in older people.

The specific objectives of this randomized controlled clinical trial is to identify and compare the impacts of traditional concurrent training and concurrent training consisting of strength training combined with dance classes on:

- Dynamic balance
- Static balance
- Seat and stand capacity
- Climb stairs capacity
- Lower limb strength
- Hand grip strength
- Muscle thickness of quadriceps
- Specific tension of quadriceps
- Cardiorespiratory capacity
- Quality of life
- Cognitive performance
- Affectivity with the intervention
- Lipid profile
- Depressive symptoms

## **METHODS**

## **Study type**

This study is characterized as a Randomized Controlled Clinical Trial, with three arms in parallel and will follow the recommendations of CONSORT 2010 Statement (SCHULZ *et al.*, 2010).

## **Population and sample**

The study will be carried out with the elderly population, who do not have disease or neuromuscular disorders. The sample will be voluntary, composed of men and women aged between 65 and 75 years, residents of the city of Porto Alegre-RS, who have not performed regular physical training for at least three months.

## **Eligibility criteria**

Inclusion criteria: Be male or female aged between 65 and 75 years old; Do not practice regular physical exercises for at least three months; No history of competitive sports throughout life; Not having musculoskeletal and neurological diseases or disorders that may influence the performance of the exercises or affect the test results; Not having health conditions in which physical exercise is contraindicated; Achieve a score of no less than 24 on the Mini Mental State Exam; Achieve a score of up to 9.11 on the Baecke Physical Activity Questionnaire.

Exclusion criteria: Miss more than 20% of training sessions; Miss more than three workouts in a row; Failure to attend any of the evaluations will be excluded from the study.

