## **Experimental design**

Initially, an interview will be carried out via telephone (or in person for volunteers who do not have access to this means of communication), in which clarifications about the study will be carried out, as well as scheduling of the first visit. The first face-to-face visit will take place at the University, in which the participants will be introduced to the responsible research subjects, will receive the informed consent form and, if they agree with all the study procedures, will be invited to sign the term in two copies. In case of acceptance, the tests referring to the inclusion criteria will be applied (Baecke's Physical Activity Questionnaire, Mini Mental State Examination and Geriatric Depression Scale), as well the socioeconomic and quality of life questionnaires. If the volunteers reach the required score, respectively below 9.11 and above 24, the second visit will be scheduled. On the second visit, blood collection will be performed to assess the lipid profile.

Afterwards, the subjects will be scheduled for the third visit, in which the quadriceps muscle thickness and quality assessment, anthropometric assessments, as well as familiarization with the lower limb strength test will be performed. Physical tests will be performed on the fourth visit. After the evaluations, the participants will be randomly allocated to one of the two interventions or the control group. After 8 weeks,

a fifth visit will be held, where the physical tests will be reassessed, as well as the application of the questionnaire on affectivity with the intervention. At the end of the 12 weeks of training, participants will be reassessed on all tests.

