## **Arms and Interventions**

*Traditional concurrent training:* The subjects will perform two sessions per week of traditional concurrent training, consisting of strength training followed by aerobic exercise over 12 weeks, with progressive intensities and training volumes. Each traditional concurrent training session will consist of specific warm-up performed on equipment for upper and lower limbs with a load of less than 30% of the training load. Then the bench press, low row, leg press, extension and knee flexion exercises will be performed. Participants will be instructed to perform the concentric phase of the movement in one second and the eccentric phase in two seconds. After strength training, aerobic training (walking outdoors or on a treadmill) will be performed with intensity based on the adapted BORG effort perception scale (ranged to 0 = minimum effort, to 10 = maximal effort).

*Concurrent training consisting of strength training combined with dance classes:* Each concurrent training session associated with dance classes will consist of the same strength training as the traditional concurrent training group, but the traditional aerobic training will be replaced by a dance class. Each dance class will consist of a 5-minute general warm-up with joint mobility exercises and dynamic stretching. Then the main part will be performed with the elaboration of choreography, lasting approximately 20 minutes. Finally, there will be a 5-minute cool-down with stretching exercises. Classes will be held in four different dance modalities, divided into four modules.

*Control group:* Subjects will be instructed to maintain their usual routine during the study period. After the end of the 12 weeks, the participants in the control group will be able to participate in one of the exercise groups according to their preference. The Control Group is necessary in this study, since some of the variables analyzed still have little evidence of the effects of physical exercise. For this reason, in addition to comparing protocols, it is also interesting to compare the results with a group that will not perform physical exercise.

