## **STATISTICAL TREATMENT**

Results will be presented as mean  $\pm$  standard deviation. The distribution of normality and homogeneity parameters will be verified using the Shapiro-Wilk and Levene test respectively. Comparison of pre-training values between groups will be analyzed using one-way Analysis of Variance (ANOVA), regardless of data distribution, as ANOVA is robust enough for this (Sawyers, 2013). The effects of training will be evaluated using two-way ANOVA (time x group). If time x group interaction is observed, an analysis will be performed using one-way ANOVA with Tukey's post hoc test for group factor and repeated measures ANOVA for time factor. Significance will be accepted when  $p \leq 0.05$ . All statistical analyzes will be performed using SPSS software (version 25.0). The eta-square values will be used to analyze the effect size: small ( $\eta^2 \geq 0.02$ ), medium ( $\eta^2 \geq 0.13$ ) or large effect size ( $\eta^2 \geq 0.26$ ) (COHEN, 1988). Individuals who do not complete the study will be analyzed using intention to treat. All assessments and data analysis will be performed by researchers blinded to the group of participants.

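### Post-randomisation exclusions for poor attendance and missed evaluations are not reconciled with the promised intention-to-treat analysis, and the attendance rules can remove only exercise-arm participants

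*Combined protocol and SAP*

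**What the plan says.** The Eligibility criteria section gives three exclusion criteria: "Miss more than 20% of training sessions; Miss more than three workouts in a row; Failure to attend any of the evaluations". The consequence is spelled out for the last of these: "Failure to attend any of the evaluations will be excluded from the study".

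The Experimental design section fixes the order of events. Four visits collect baseline data, and then "After the evaluations, the participants will be randomly allocated to one of the two interventions or the control group". At week 8 "a fifth visit will be held, where the physical tests will be reassessed", together with the affectivity questionnaire. Finally, "At the end of the 12 weeks of training, participants will be reassessed on all tests".

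Under Arms and Interventions, the traditional arm trains on a stated schedule: "The subjects will perform two sessions per week of traditional concurrent training", for 12 weeks. No weekly frequency is given for the dance arm. Controls keep to their usual routine and have no sessions in that period.

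The Statistical treatment section names a two-way time-by-group ANOVA, followed if there is an interaction by one-way and repeated-measures ANOVA. On incomplete participation it says only: "Individuals who do not complete the study will be analyzed using intention to treat". The Sample size section adds three people per group for losses (9 to 12 per group, 36 in total).

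**The concern.** An intention-to-treat analysis keeps every randomised person in the allocated group. The exclusion rules remove randomised people for what they do after allocation, and no sentence connects the two statements. Two analysts could follow this plan faithfully and analyse different people.

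The removal is also uneven. Attendance at training can be failed only by someone assigned to train. Applying the rules leaves exercise arms filtered on adherence beside a control arm that is not, so the exercise-versus-control comparisons lose the protection of randomisation. Dance versus traditional training is exposed too if adherence differs between those arms. Spare recruitment replaces numbers but does not restore comparability.

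**Working it through.** **When each rule can act**

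| Rule | Before randomisation | After randomisation | Arms affected |
|---|---|---|---|
| More than 20% of sessions missed | no | yes | two exercise arms only |
| More than three workouts missed in a row | no | yes | two exercise arms only |
| Any evaluation missed | yes (visits 1–4) | yes (weeks 8 and 12) | all three |

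The missed-evaluation rule is legitimate at visits 1–4. Its later use is a post-randomisation exclusion.

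**Whether intention to treat can be carried out as written.** On the charitable reading, the eligibility section ends participation and the statistical section governs analysis. But no section says that excluded people attend later evaluations, so they would have no later values. No missing-value method is stated, and a conventional repeated-measures ANOVA drops people with a missing visit. The result would be a complete-case analysis under an intention-to-treat label. The commitment to CONSORT 2010 under Study type adds no rule in this text on who is evaluated or analysed.

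**A side effect.** Because missing any evaluation leads to exclusion, missing week 8 also removes a person from outcomes not scheduled then, such as lipids and muscle thickness.

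**How many people the attendance rules could remove (illustration)**

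From the documents: 2 sessions × 12 weeks = 24 (stated for the traditional arm, assumed for dance); 12 people per arm; allowance of 3 losses per group. Since 20% of 24 = 4.8, exclusion follows 5 or more missed sessions, or 4 in a row.

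Assumed, because the documents give no figure: mean absence q per session, and either independent absences, X ~ Binomial(24, q), or absences varying between people, X ~ beta-binomial with intraclass correlation (ICC) 0.2. The quantity is P(X ≥ 5), times 12 for the expected number per exercise arm.

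| Mean absence q | Independent: P, people of 12 | ICC 0.2: P, people of 12 | P across ICC 0.05–0.3 |
|---|---|---|---|
| 5% | 0.006, 0.1 | 0.090, 1.1 | 0.046–0.092 |
| 10% | 0.085, 1.0 | 0.195, 2.3 | 0.157–0.195 |
| 15% | 0.287, 3.4 | 0.307, 3.7 | 0.289–0.319 |
| 20% | 0.540, 6.5 | 0.420, 5.0 | 0.385–0.492 |

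Controls lose nobody to these two rules. The consecutive-absence rule adds almost nothing in these models, but they leave out clustering of absences in time.

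Sensitivity to the unstated dance frequency, at 10% absence:

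- 12 sessions (exclusion at 3 missed): 0.111 independent, 0.179 with ICC 0.2.
- 36 sessions (exclusion at 8 missed): 0.024 independent, 0.170 with ICC 0.2.

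**What selection could do (illustration).** Suppose there is no true effect, the least adherent fraction e of each exercise arm is excluded, and adherence correlates r with outcome. The apparent benefit over control is r·φ(z)/(1 − e) standard deviations, where z = Φ⁻¹(e).

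- e = 0.10, r = 0.2: 0.2 × 0.1755 / 0.90 = 0.04 SD.
- e = 0.30, r = 0.5: 0.5 × 0.3477 / 0.70 = 0.25 SD.

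Over that range, a simulated three-arm ANOVA on change with 12 randomised per arm had type I error of about 0.052 to 0.079 against a nominal 0.05. Both e and r are assumptions, including the positive sign of r.

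**The case against.** The strongest defence is that the statistical section is the only one governing analysis and that it addresses this group: a person removed under the eligibility rules is naturally a non-completer, and non-completers are promised intention to treat. Someone excluded after week 8 already has baseline and week-8 physical tests. That excluded people are not evaluated later is inferred from silence, and the wording about exclusion from the study attaches grammatically only to the missed-evaluation rule.

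Part of this stands. Intention to treat is not impossible in principle; it is not workable as the text is written. The attendance rules do sit under the same exclusion heading, however, and the missing-value method is absent on any reading. No section resolves the conflict.

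The objections to the numbers also stand in part. That losses exceed three at 15% absence depends on 24 sessions: with 36, the expected loss is 1.9 of 12 (independent) or 2.98 (ICC 0.05). If absences cluster in time, with an assumed lag-1 correlation of 0.5, the consecutive-absence rule adds about 0.02–0.03 to the exclusion probability. The possible bias is modest at the low end of the assumed range. The case therefore rests on the contradiction, not on these figures.

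**Conclusion.** The concern holds and needs correcting before the analysis is fixed. A stated rule removes randomised people, two of its three parts can act only in the exercise arms, and the intention-to-treat promise has neither the follow-up nor the method to cover them. It decides who enters every efficacy comparison, and week-8 and week-12 values that are not collected cannot be recovered later.

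Under the assumed 24 sessions, the attendance rules alone stay within the three-loss allowance on average at 5–10% absence and exceed it at 15% or more. That describes how many people could be lost. The size and direction of any bias cannot be derived from the documents, which give no data on adherence or its relation to outcome.

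**What to change.** Reconcile the Eligibility criteria and Statistical treatment sections:

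1. Limit the missed-evaluation exclusion to evaluations before randomisation.
2. State that attendance is not a ground for ending evaluations or for removal from the analysis, for example: *All randomised participants are invited to the 8- and 12-week evaluations and are analysed in their allocated group.* Whether a poor attender continues training is left to the investigators.
3. Name a time-by-group method that keeps people with a missing visit. A likelihood-based mixed model with a small-sample correction is one suitable choice.
4. Use the existing 20% and consecutive-absence thresholds only to define a secondary per-protocol sensitivity analysis, applied to each exercise arm's own scheduled sessions. State the dance arm's number of sessions so that this can be done.
5. Report attendance and losses by arm.

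Items 1 to 3 are the essential repair. The cost is revised wording, continued invitations of non-attenders to two evaluations already scheduled, and slightly more analysis work. No extra participants are needed. The mixed model relies on a missing-at-random assumption, which should be stated.

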## **Sample size**

The sample calculation was performed based on the study by Rodrigues-Krause *et al.*, (2018) for the gait ability variable (TUG) (total n = 27, i.e. n = 9 individuals per group). The calculation was performed using the GPOWER version 3.1.9.4 program, in which  $\alpha = 0.05$  and power of 95% were adopted. Anticipating possible sample losses, three more individuals will be added to each group (total n = 36).

## **Recruitment**

Participants will be recruited through publicity using posters that will be posted at University, as well as published on the researchers' social media with the email and their personal phone. The responsible researchers will evaluate the eligibility criteria and verify if the individual has the necessary characteristics to participate in the project.

## **Randomization**

Participants will be randomized into groups through <https://www.random.org/>. The person who will carry out the randomization will not be one of the researchers responsible for the evaluations. Participants will be informed of their group before starting training. Individuals who are randomly assigned to the control group, after the 12-week period, will be able to choose to participate in one of the physical exercise groups according to their preference.

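### The randomisation text neither secures 12 per arm nor protects sex balance, and the analysis of strength outcomes in a mixed-sex sample of 36 has no sex term

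*Combined protocol and SAP*

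**What the plan says.** All places are in the combined protocol and SAP.

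- **Study type:** a randomised trial "with three arms in parallel".
- **Sample size:** the calculation gives "total n = 27, i.e. n = 9 individuals per group" at 95% power. For losses, "three more individuals will be added to each group (total n = 36").
- **Randomization:** "Participants will be randomized into groups through" a public random-number website. The section adds: "The person who will carry out the randomization will not be one of the researchers responsible for the evaluations".
- **Experimental design:** "After the evaluations, the participants will be randomly allocated to one of the two interventions or the control group".
- **Population and sample:** the sample is "composed of men and women aged between 65 and 75 years". No expected share of men is given.
- **Outcome measures:** these include knee-extension 1RM, handgrip strength, knee-extension power and quadriceps thickness.
- **Statistical treatment:** training effects are tested by a time x group ANOVA. Only if that interaction appears does a one-way ANOVA by group follow, with Tukey comparisons. No sex term and no baseline covariate is mentioned.

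No section states the sequence type, allocation ratio, block size, stratification factors, or whether a list is made in advance.

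**The concern.** The sample size is stated per arm, but nothing in the allocation procedure fixes the arm sizes. If each person is assigned independently, 36 people can split quite unevenly, and the allowance of three per group for losses may be used up before training starts.

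Sex is a separate matter. Strength, power and muscle thickness can be expected to differ between men and women. With about 12 per arm and no stratification, one training arm can easily receive several more men than the other. The follow-up comparison that would show whether dance differs from traditional training has no term to absorb that.

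**Working it through.** **1. The plan's own figure.** 3 x 9 = 27 and 27 + 3 x 3 = 36, so the total of 36 reproduces. The 27 cannot be rebuilt because the Sample size section gives no effect size or SD.

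**2. Arm sizes, if allocation is simple (assumed).** With 36 people and three arms at probability 1/3 each, P(a, b, c) = 36! / (a! b! c!) / 3^36. Summing exactly:

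| Event, before any losses | Probability |
|---|---|
| 12/12/12 | 2.3% |
| Some arm below 9 | 31% |
| Largest minus smallest arm at least 6 | 49% |

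If a full list of 36 is split equally, the arms are 12/12/12 and none of this applies.

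**3. What that means for precision.** The variance of a two-arm difference is proportional to 1/a + 1/b. The 9 v 9 comparison behind the sample size gives 2/9 = 0.222. An 8 v 12 comparison gives 1/8 + 1/12 = 0.208, which is still better. Applying this rule to the same distribution:

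- P(dance v traditional less precise than 9 v 9) = 6.0%.
- P(at least one of the three pairs less precise than 9 v 9) = 13%.
- The average variance increase over 12 v 12 is 6.6%.

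**4. Sex balance at exactly 12/12/12.** Let M be the number of men among the 36 (not stated, so a range is used). The probability of x and y men in the two training arms is C(12,x) C(12,y) C(12,M−x−y) / C(36,M). Summing over |x − y| ≥ 3:

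| Men of 36 (assumed) | P(training arms differ by 3 or more men) |
|---|---|
| 9 | 24.6% |
| 12 | 28.6% |
| 18 | 31.4% |

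Three men in 12 is 25 percentage points. Under simple allocation, a gap of at least 25 points in the proportion of men between the training arms has probability 18.5%, 22.1% and 25.0% for the same three mixes (simulation). Fixing the arm sizes therefore does not remove the problem.

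**5. Effect on a comparison of raw post-training values.** Assume a male–female gap of g = 1 to 2 within-sex SDs; the documents give no figure.

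- Chance difference from a 3-man imbalance: (3/12) x g = 0.25 to 0.50 within-sex SD.
- Error variance without a sex term, relative to a model with one: 1 + p(1 − p)g², where p is the share of men. At p = 0.25 and g = 1 this is 1 + 0.1875, about 19% larger. At p = 0.5 and g = 2 it is 1 + 1.00, or 100% larger.
- In the mixed-sex SD that the unadjusted ANOVA uses, the same difference is 0.25/√1.25 = 0.22 to 0.50/√1.75 = 0.38.

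**6. Effect on the time x group test.** This test compares change. A sex gap that is the same before and after training drops out of each person's change, and so out of the interaction. What remains is any difference between men and women in absolute gain, for example in kilograms of 1RM.

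**The case against.** A reader might infer that participants are allocated one by one, and that the arms will therefore be unequal. The documents do not say so. The Experimental design section speaks of participants in the plural being allocated after the evaluations, and the Sample size section fixes numbers per group. Both fit an equal split of a complete list. On arm sizes alone, the plan is missing a description; it is not shown to be defective.

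A reader might also take the 31% chance of an arm below 9 as a 31% chance of losing the planned precision. It is not: with 36 people, a small arm is partly offset by a larger one, and the relevant figure for dance versus traditional training is about 6% before losses.

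On sex, it is fair to say that the main test uses change, that the group-wise ANOVA is run only after an interaction, and that randomisation keeps the comparison valid on average. In simulation at 12/12/12 with sex gaps of 1 or 2 SD, unadjusted type I error stayed at 4.8–5.1%. The planned baseline comparison might reveal an imbalance. By the figures above, 69–75% of trials would have a difference smaller than 3 men.

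All of that stands, and it limits the harm. It does not remove the point. A baseline test does not correct an imbalance, the step that identifies which arms differ is unadjusted, and that step carries the precision loss in every trial, balanced or not.

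**Conclusion.** The concern holds in a limited form. The plan does not secure the 12 per arm that it counts on, and it leaves sex balance to chance in a sample of 36 with several strength-related outcomes.

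The arm-size figures (2.3% and 31%) hold only under simple allocation. The sex figure of 25–31% is computed at 12/12/12 and assumes 9–18 men. The risk remains, somewhat smaller, if allocation is simple. The consequence of 0.25–0.50 within-sex SD for a 3-man imbalance, and of 19–100% more error variance, rests on an assumed sex gap of 1–2 SD. It applies to the follow-up one-way ANOVA if that is run on raw values, which the plan does not specify.

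The stronger reading, that an excess of men would bias the trial's main result, is not supported. The imbalance is random, and a constant sex difference largely cancels in the time x group test. The change is still worth making because it costs almost nothing, and a restricted sequence cannot be added once people have been allocated.

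**What to change.** **Randomization section.** State a 1:1:1 list generated in advance, in permuted blocks of 3 and 6 in random order, separately for men and women. The non-assessor already described there holds it and releases one assignment at a time after baseline. Block sizes should be kept from those who recruit. If an equal split of a full list was intended, the section should say so, and the split should be made within sex.

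**Statistical treatment section.** Include sex in the between-arm follow-up analyses and sex x time in the time x group model. Blocking alone would fix arm sizes but not sex balance, so both changes are needed. If allocation has already taken place, report the method used; the sex terms can still be specified.

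**Cost.** Minutes to make the list, and a sentence or two in each section. The sex terms use one or two degrees of freedom. Unfinished blocks can leave the arms slightly unequal. Simulating this scheme for 36 people with an expected one-third men gave equal arms in about 41% of draws, a largest gap of two in about 55%, and three or four in about 4%. No arm fell below 10, and the training arms never differed by more than 2 men.
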